#### Alternative strategies:

For our primary analysis, if CBF or CVR is not normally distributed based as shown in Q-Q plot, a nonparametric Wilcoxon rank-sum test will be used instead. And for our secondary analysis, if we are not powered to identify correlations of biomarkers with subdomains of symptoms and neuropsychological CDEs after multiple comparison correction, we will use dimension reduction approaches such as principal component regression (PCR) on CDEs to group panels of symptom assessments. The resulting panels of symptoms are selected to explain most of the variations across subjects and will be most correlated with brain biomarkers.

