## 4.2.2 SECONDARY ENDPOINT:

To determine if sildenafil reduces the blood/saliva levels of brain biomarkers of iniury after concussion. The goal of this study is to produce pilot efficacy data to design a definitive study aimed at testing the efficacy of the administration of sildenafil at reducing the blood/saliva levels of Von willebrand factor (vWF), glial fibrillary acidic protein (GFAP), neurofilament-H (NFL-H), creatine kinase-B (CKBB) and tau. In brief, about 8cc of blood and saliva will be collected at each time-point. The blood and saliva will be collected once at baseline and on day 1-3 and 30 after injury. Upon collecting the samples, the blood will be centrifuged at 4 degrees Celsius for 10 minutes at 1500 rpm. The plasma/saliva will be collected and aliguoted into 1 ml tubes and immediately frozen at -80 degrees Celsius. To measure the levels of brain biomarkers, the plasma levels of vWF, GFAP, NFL-H, CKBB, and tau will be measured using the enzyme-linked immunoassay according to the manufacturer's instructions. Each sample will be loaded onto the 96-well plate in triplicate. Each sample will be tested in triplicate. The plate will be incubated for 2 h at room temperature, washed, and 200 µl of the substrate will be added for 90 min at room temperature. After 90-min, the absorbance will be detected at 405 nm. The values will be compared to the standard curve and the concentration of the biomarker will be determined.

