Also, we will assess the treatment effect of sildenafil on post-concussive symptoms and cognitive performance using two-sample t-test similarly as in the primary aim, but with the secondary endpoints of symptoms. On day 1 and 30 after injury we will then calculate the difference in CBF/CVR and each of the post-concussive symptom assessments and cognitive assessments after the single treatment of sildenafil. Also, we will assess the post-concussion correlations of CBF/CVR and cognitive performance by calculating the cross-sectional Pearson correlations of CBF/CVR with symptom inventory and neuropsychological CDEs collected at Day 1 and 30 after TBI. Correlations will be calculated separately and jointly at each time point, and for each of the subdomains of neuropsychological CDEs. Multiple comparisons will be adjusted by controlling the false discovery rate (FDR).

Our secondary analyses will consist of assessing the treatment effect of sildenafil therapy on brain biomarker levels using two-sample t testing, but with the secondary endpoints of symptoms. We will then calculate the difference in brain biomarker levels at the beginning of the sildenafil therapy and after the treatment period (Day 30 vs Day 1-3). Scatter plots including both arms will be generated based on the calculated differences and two linear regression models with changes in brain biomarkers as outcomes, and changes in symptoms as independent variables will be fit to assess the association between the recovery of the TBI-related markers. Potential confounders such as gender and treatment arm indicator will be adjusted in the model.

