#### Power analysis and sample size justification

We conducted a power analysis based on the primary endpoints of change in CVR and CBF and correlation of CBF/CVR and symptoms/cognition. Based on the preliminary results, we assume the average changes in CVR between treatment and placebo has an effect size of 0.86. With 50 concussed boxers in each arm, assuming that the correlation between the outcome measures at Day 1-3 and 30 is 0.2, we will achieve 80% power to detect difference in CVR changes comparing sildenafil and placebo effects. If the correlation is 0.5 among outcome measures at all time-points, then with 80% power we only need 34 concussed boxers in each arm. Table 1 demonstrates the needed sample size under a range of effect sizes and within-subject correlations. To understand the correlation between the CVR and post-concussive symptoms among the 50 enrolled boxers (for each group) assessed at three time points, we will have 82.9% power to detect a correlation of 0.4 based on the preliminary results in Table 1 with 95% confidence level.

	Correlation between 3, time-points (rho)							
	0	0.2	0.3	0.5	0.6	0.7	0.8	
Corresponding SD	1.414	1.265	1.183	1	0.894	0.775	0.632	
Effect size	Sample size needed							
0.7	46	38	33	25	21	16	12	
0.86	32	26	23	18	15	12	9	
1	24	20	18	14	12	10	8	
1.2	18	15	14	11	9	8	6	

Table 1: Sample size for each treatment and placebo group under a range of effect sizes and within-subject correlations to achieve 80% power.

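### The principal-component fallback for biomarker-symptom associations is in practice triggered by failed corrected tests, is not placed in the corrected family, and credits components with a property they lack.

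*Combined protocol and SAP*

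**What the plan says.** All references are to section 10.1 unless stated.

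- **Trigger** (Alternative strategies): the fallback applies "if we are not powered to identify correlations of biomarkers with subdomains of symptoms and neuropsychological CDEs after multiple comparison correction".
- **Method** (same paragraph): "we will use dimension reduction approaches such as principal component regression (PCR) on CDEs to group panels of symptom assessments". The number of components, the rule for keeping them and the handling of multiplicity are not given.
- **Property claimed for the panels** (same paragraph): "The resulting panels of symptoms are selected to explain most of the variations across subjects and will be most correlated with brain biomarkers".
- **Named correction** (Statistical analyses): "Multiple comparisons will be adjusted by controlling the false discovery rate (FDR)". This sentence closes the paragraph on symptoms, cognition and their correlations with CBF/CVR. No FDR level is stated.
- **Planned biomarker-symptom analysis** (next paragraph): "two linear regression models with changes in brain biomarkers as outcomes, and changes in symptoms as independent variables will be fit". No correction is named there.
- **Biomarkers** (section 4.2.2): five, since "the plasma levels of vWF, GFAP, NFL-H, CKBB, and tau will be measured using the enzyme-linked immunoassay".

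**The concern.** There are two problems.

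First, the fallback depends on results. The trigger speaks of power, but the power section covers only CBF/CVR change and the CVR-symptom correlation. With no power figure for biomarker correlations, the condition can be judged only by looking at the corrected tests and finding that they failed. The question of whether biomarkers relate to symptoms and cognition is then asked again of the same data, and nothing says that the new tests share the error budget of the first round.

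Second, the sentence about the panels joins two aims that differ. Principal components maximise variance among the scores and never use the biomarkers. A reader who trusts the sentence will over-interpret the leading component. An analyst who tries to make it true will choose panels by their observed correlation and then report p-values that ignore the choice.

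At stake is the credibility of any biomarker-symptom association reported from the fallback. Section 4.2.2 describes the biomarker work as groundwork for a definitive study, so a spurious panel could be carried forward.

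**Working it through.** **1. The plan's own figure.** The power section considers the "correlation between the CVR and post-concussive symptoms among the 50 enrolled boxers (for each group)" and states that "we will have 82.9% power to detect a correlation of 0.4 based on the preliminary results in Table 1 with 95% confidence level". By Fisher's z, two-sided:

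Φ(atanh(0.4) × √(50 − 3) − 1.96) = Φ(0.4236 × 6.856 − 1.96) = Φ(0.944) = 82.8%.

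The stated 82.9% is reproduced. It is for one uncorrected test of CVR against symptoms, not for biomarkers.

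**2. How likely the fallback is to be reached.** Borrow r = 0.4 for a biomarker correlation (an assumption). Use the Bonferroni threshold 0.05/m, which is the strictest step of the Benjamini-Hochberg FDR procedure. With n = 50, power is Φ(2.904 − z):

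| Tests m | z | Power |
|---|---|---|
| 5 | 2.576 | 63% |
| 25 (5 biomarkers × 5 scores) | 3.090 | 43% |
| 50 (5 × 10) | 3.291 | 35% |

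With both groups pooled (n = 100), 0.4236 × √97 = 4.172, and power is Φ(1.082) = 86% for 25 tests and Φ(0.882) = 81% for 50. The fallback is a realistic outcome at n = 50 and less so at n = 100.

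**3. Do variance-selected components correlate most with the biomarker?** Take 8 scores with pairwise correlation 0.5 (an illustration). The first eigenvalue is 1 + 7 × 0.5 = 4.5, so the first component explains 4.5/8 = 56% of the variance. It correlates √(4.5/8) = 0.75 with each score. Let the biomarker correlate 0.4 with its true source:

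| Biomarker follows | First component | Best single score |
|---|---|---|
| the shared factor | 0.40 | 0.4 × 0.75 = 0.30 |
| one score | 0.4 × 0.75 = 0.30 | 0.40 |
| the difference of two scores | 0.00 | 0.4 × 0.5 = 0.20 (absolute value) |

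The claimed property holds in the first case only.

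**4. Error rate with no true association.** The documents supply the five biomarkers and n = 50 per group. The following are assumed because the SAP is silent: 5 or 10 scores, their intercorrelation, the retention rule, a 5% FDR level, n = 100 as an alternative, and a first stage made of all pairwise correlations. With no true association, the FDR equals the chance of at least one false claim, so 5% is the benchmark.

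Grid A keeps 1 to 3 components, with intercorrelation 0.3 or 0.5 (4,000 runs per setting; Monte Carlo standard error near 5% is √(0.05 × 0.95/4000) = 0.3 points). Grid B keeps components up to 70% of variance, with intercorrelation 0.4.

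| Procedure | Grid A | Grid B |
|---|---|---|
| Corrected subdomain tests only | 3.9-5.5% | 4.7-5.7% |
| Then fallback with its own FDR | 6.1-9.2% | 8-9% |
| Then fallback uncorrected | 22-55% | 49-69% |
| One FDR family over both sets | 3.9-5.3% | 4.4-5.1% |

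Comparing like with like inside each Grid A setting, a separately corrected fallback adds 2.2 to 4.1 percentage points.

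Closed-form check of the uncorrected rows: 1 − 0.95^(5k) is 22.6%, 40.1% and 53.7% for k = 1, 2 and 3 components, and 1 − 0.95^20 = 64.2% for k = 4.

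**5. If panels were picked by correlation with the biomarkers.** Taking the best component per biomarker, with FDR applied only across biomarkers, gives 15-24% (Grid B). Searching all components without adjustment gives 73% with 5 scores and 93% with 10. The closed forms 1 − 0.95^25 = 72.3% and 1 − 0.95^50 = 92.3% agree.

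**The case against.** A reader might infer that the SAP lets the fallback escape FDR control. The documents do not say so. They are silent on correction at that step, and the one FDR sentence sits in the paragraph before the biomarker analyses. The reference to correction in the trigger shows that the authors intended some control of error, but not by what method, at what level or over which family. If the FDR sentence is read as general and applied separately to the fallback, the inflation is modest.

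A reader might also infer that the secondary endpoint could be won through this route. It could not. The Outcomes paragraph defines that endpoint as the effect of sildenafil on biomarkers, compared by two-sample t-tests, which the fallback does not touch.

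Three further points are fair. Reducing the number of scores is a recognised response to multiplicity, and the SAP discloses it in advance. Component-level associations are not identical to subdomain-level ones. The larger error rates depend on inputs that the SAP does not give, and the simulated first stage is a construction, since the SAP itself plans two regressions and only alludes to subdomain correlations.

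These points limit the size and reach of the problem but do not remove it. Every two-stage version that was simulated exceeded the error rate of its own first stage, and the claim about the panels fails on either reading.

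**Conclusion.** The point stands as a defect in an ancillary analysis. The statement that variance-selected panels will be most correlated with the biomarkers is wrong as a guarantee; it can be true when a biomarker follows the factor shared by all scores. The fallback is a second, results-dependent look whose tests are not placed in the corrected family.

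Under no association, the chance of at least one false claim goes from about 5% to about 6-9% with a separate FDR correction at the fallback, and to about 22-69% with none. The upper figures belong to rules that keep more components. They rest on the assumed number of scores, intercorrelation, retention rule and FDR level, and on reading the SAP's silence as no correction, so they show what the text permits and do not predict what will be done. The primary endpoints and the randomised comparison of biomarker levels are unaffected.

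**What to change.** Rewrite the one paragraph under Alternative strategies:

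- Delete the clause saying that the panels will be most correlated with the biomarkers.
- Remove the failure trigger. Derive the components once from the symptom and cognitive scores, by a fixed variance rule and without reference to biomarker data.
- Test the components together with the subdomains in one FDR family, and state the level. In the simulations this holds the false-claim rate at about 4-5%.
- Alternatively, keep the step as a fallback but label it exploratory, with no confirmatory claim.

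This needs no new data, staff or participants. The cost is slightly stricter thresholds for the subdomain tests under the single-family option. Under the exploratory option, a panel found by the fallback cannot be reported as confirmed.

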#### **Stopping rules**

We do not anticipate a stopping rule for efficacy as the primary and secondary endpoints of the proposed study are clinically important, but intermediate. Even if we cannot reject the null hypothesis for the primary end point, we have multiple secondary endpoints that could still benefit our understanding towards the effect of sildenafil on concussed injury. Data collected in this study will be used to conduct a power analysis to design and implement the definitive study.

#### Sensitivity analyses and missing data

Although we do not expect large amount of missing data due to the close monitoring of the study implementation and great compliance rate from the past study experiences, we will perform sensitivity analyses to assess the potential impact of missing data. Since the analytic methods proposed in the primary and secondary aims will base on the missing at random (MAR) assumption, we will investigate the amount and patterns of missing data, and their influence on the final estimates. We will compare the rate of missing observations between the treatment and placebo groups using Fisher's exact tests. We will also evaluate model estimates using complete data only and data with imputed values to see whether the results suggest bias in analysis of the available data. For possible missing values that are "non-ignorable", we will utilize methods that jointly model the missing mechanism and the time-dependent outcomes to conduct valid statistical inference. In particular, shared parameter models, pattern-mixture models and potentially joint modeling of survival and longitudinal analysis methods could be used to assess potential impact of missing data. Shared parameter models link the outcome and missing probabilities using latent variables (random effects), and a logistic regression will

be used to estimate the probability of missing at each time point. While pattern-mixture models allow separate models for observations with different patterns of missingness. Results obtained from the shared parameter and pattern-mixture models will be compared to the estimates from the analysis under the MAR assumption. Statistical software including SAS and R will be used for the analysis.

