## 7.2 LABORATORY PROCEDURES/EVALUATIONS

## 7.2.1 CLINICAL LABORATORY EVALUATIONS

#### Biochemistry:

Blood (~8cc) will be collected and the blood albumin, alkaline phosphatase, total bilirubin, bicarbonate, BUN, calcium, chloride, creatinine, glucose, LDH, phosphorus, potassium, total protein, SGOT [AST], SGPT [ALT], sodium, and coagulase levels will be measured from from the participants at day 1-3 and 30 after injury. By performing these tests we will be able to detect side effects that may be associated with the study drug. For example, if the AST or ALT ratio is out of the normal range, the participant(s) will be withdrawn from the study. Also, if the participant reports any side effects that may be linked to the study drug, the study participant will be withdrawn from the study. The IRB and FDA will be notified within 7 business days. The

testing will be performed by Quest diagnostics, Dallas, Texas. Blood will also be collected to measure the levels of brain biomarkers of injury within the athletes.

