#### Outcomes

**Primary endpoints-** The absolute changes in global and regional CBF/CVR to hypercapnia and improved symptoms and cognitive performance.

Secondary endpoints- Effect of sildenafil on brain biomarkers in blood after injury.

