#### **Statistical analyses**

Preliminary analyses: Prior to the formal analyses, we will conduct exploratory data analysis by examining the distributions of the key variables using descriptive statistics and graphic tools. In particular, baseline variables (demographics, concussion history and injury severity characteristics) will be examined to determine whether outliers are present. The baseline characteristics of the 100 enrolled boxers/MMA fighters will be compared with 80 controls using linear regression and two sample testing. Continuous variables (primary and secondary outcomes) will be summarized through standard measures of central tendency and spread including means, medians, standard deviations and IQRs. Frequency distributions will be calculated for categorical variables (CBF/CVR, post-concussion symptoms,

neuropsychological measurements). Data transformations will be used if needed to produce variables that conform to the distributional assumptions underlying the analytic techniques. Both primary and secondary outcomes will be evaluated under the intent-to-treat principle, meaning that all available data on all randomized participants, regardless of adherence to the study protocol, will be included and analyzed according to the treatment assignment, although compliance will be closely monitored via pill counting. Statistical analysis will be performed with SAS (SAS Institute, Cary, NC, USA) and R software.

Primary analyses: Our primary analysis (**Aim 1**) will be driven by the primary hypothesis that administration of single or multiple doses of sildenafil will improve CBF/CVR, lower symptoms and improve cognition. Boxplots of CBF and CVR of concussed boxers after sildenafil and placebo periods will first be plotted and compared with values at Day 1-3 and 30 post-TBI as well as with the 80 controls.

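### The SAP claims to rest on missing at random, but the treatment tests it names are two-sample tests on available changes, which are not generally valid under that assumption; the size of any bias is unknown

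*Combined protocol and SAP*

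**What the plan says.** The missing-data part of SAP section 10.1 states that "the analytic methods proposed in the primary and secondary aims will base on the missing at random (MAR) assumption". It plans a comparison of missingness rates between arms, a comparison of complete-data with imputed-data estimates, and possible shared-parameter and pattern-mixture models. The results of those models are to be set against the MAR estimate.

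The treatment comparisons appear elsewhere in section 10.1:

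- Outcomes gives the primary endpoints: "The absolute changes in global and regional CBF/CVR to hypercapnia and improved symptoms and cognitive performance".
- Statistical analyses compares symptoms and cognition "using two-sample t-test similarly as in the primary aim". The secondary analysis consists of "assessing the treatment effect of sildenafil therapy on brain biomarker levels using two-sample t testing", followed by differences in biomarkers between Day 1-3 and Day 30.
- Alternative strategies adds that, if CBF or CVR is not normally distributed, "a nonparametric Wilcoxon rank-sum test will be used instead".
- On the analysis set, "all available data on all randomized participants, regardless of adherence to the study protocol, will be included".

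No mixed model, other likelihood-based repeated-measures model or multiple imputation is named as the main analysis. Mixed-model texts and a paper on baseline as covariate appear only in the SAP's reference list.

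On withdrawal, protocol section 7.2.1 says that "if the participant reports any side effects that may be linked to the study drug, the study participant will be withdrawn from the study" and that "if the AST or ALT ratio is out of the normal range, the participant(s) will be withdrawn from the study".

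**The concern.** A two-sample test on changes drops anyone who lacks one of the two values. Someone who attends Day 1-3 and is withdrawn before Day 30 contributes nothing, although the Day 1-3 value was observed. Under MAR, missingness may depend on observed values, and an analysis that discards them does not in general have the property the SAP claims.

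The withdrawal rule makes this more than a matter of wording. It removes people from the study, not only from the drug, for events expected more often on sildenafil. The early-termination visit in section 7.3.3 is written for the study ending early, and no Day 30 collection is described for a withdrawn participant.

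Two things are at stake. The main estimate may lack the validity claimed for it. The shared-parameter and pattern-mixture results would also be compared with a reference analysis that the SAP never defines.

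**Working it through.** **1. Which test is specified.** For symptoms, cognition and biomarkers the t-test is named. For CBF and CVR it is inferred from the cross-reference to the primary aim and from the rank-sum fallback, because the primary-analysis paragraph itself describes only boxplots. The biomarker-on-symptom regressions are not treatment comparisons and are outside this point.

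**2. When a test on available changes is unbiased.** Let Y0, Y1 and Y2 be the pre-fight, Day 1-3 and Day 30 values, each with SD 1, normally distributed, with no treatment effect. Let ρ01 and ρ12 be the correlations of Y1 with Y0 and with Y2. Let withdrawal before Day 30 depend on Y1, which is observed, so the data are MAR. Let Δ be the mean of Y1 among sildenafil participants who stay, minus the same mean on placebo. Then:

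- change from Day 1-3 to Day 30: bias = (ρ12 − 1)Δ
- change from pre-fight to Day 30: bias = (ρ12 − ρ01)Δ

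Both are zero when Δ = 0. That holds if data are missing completely at random, if missingness depends on arm alone, or if withdrawal acts in the same way and at the same rate in both arms.

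**3. The SAP's own correlation structure.** The SD row of the sample-size table reproduces as √(2(1 − ρ)): √1.6 = 1.265 at ρ = 0.2 and √1 = 1.000 at ρ = 0.5. The SAP therefore works with changes in units of one measurement's SD and a single ρ across the three time-points. With ρ12 = ρ01, the bias in change from pre-fight to Day 30 is exactly zero. A simulation agrees (6000 trials, 50 per arm, 21% v 10% withdrawal, ρ 0.2 and 0.5): bias within 0.003 SD and type I error 4.6-4.9%. The bias in change from Day 1-3 to Day 30 becomes (ρ − 1)Δ, which is not zero.

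**4. Size for change from Day 1-3 to Day 30.** Suppose a proportion p with the highest withdrawal propensity leave, and that propensity correlates λ with Y1. The mean of Y1 among those who stay is −λφ(z)/(1 − p), where z is the (1 − p) normal quantile.

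- p = 0.16: 0.2433/0.84 = 0.290
- p = 0.04: 0.0862/0.96 = 0.090
- Δ = −(0.290 − 0.090)λ = −0.200λ
- Bias = (1 − ρ) × 0.200λ. For λ = 1 this is 0.16 at ρ = 0.2 and 0.10 at ρ = 0.5. For λ = 0.3 it is 0.048 and 0.030.
- Against the SAP's assumed effect of 0.86: 0.030/0.86 = 3% to 0.16/0.86 = 19%.

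Simulation of the t-test on this change (6000 trials per scenario, 50 per arm, no true effect, two-sided 5%, ρ 0.2 and 0.5, λ 0.3 to 1.0):

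| Assumed withdrawal, sildenafil v placebo | Bias (SD) | Type I error |
|---|---|---|
| 10% v 10% | 0 | 4.4-5.2% |
| 20% v 10% | 0.02-0.13 | 5.2-7.7% |
| 16% v 4% | 0.03-0.16 | 4.9-9.5% |
| 50% v 14% | 0.08-0.43 | 6.0-31% |

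The 16% v 4% row borrows the headache rates in protocol Table 4. The last row sums every event in that table with no overlap, so it is an upper bound. The documents give none of these as withdrawal rates, and they give no value for λ. The direction is also assumed: higher Day 1-3 values leave more often, and the sign flips if lower values do. A likelihood estimator that uses all Day 1-3 values stayed within ±0.006 SD, with type I error 4.4-5.4%, in all 26 scenarios (these rows plus no withdrawal).

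**5. Precision.** A change from pre-fight baseline has variance 2(1 − ρ) per participant; a baseline-adjusted outcome has 1 − ρ². The ratio is (1 + ρ)/2, which is 0.60 at ρ = 0.2 and 0.75 at ρ = 0.5.

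**The case against.** Unequal withdrawal alone does not bias a t-test. Withdrawal must also depend on the outcome, and nothing in the documents links side effects to Day 1-3 CBF or CVR. That stands, and it is why no size can be fixed.

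A reader might multiply the Table 4 headache rates by 50 per arm and infer about 8 v 2 withdrawals. The documents do not support that. Section 8.3 lets physician-investigators prescribe for headache, so not every headache need end participation. Table 7, with repeated daily dosing, shows a narrower gap (39% on placebo, 42-49% on sildenafil). Nor can the AST/ALT rule be assumed to separate the arms, because Table 5 lists abnormal liver tests among events equally common on placebo.

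A reader might also infer a bias of about 0.08 to 0.15 SD in change from pre-fight baseline. That requires a correlation of 0.2 with baseline but 0.5 to 0.8 between the post-injury visits, together with outcome-dependent dropout on sildenafil only. The SAP assumes one common correlation, under which this bias is zero. With the same dependence in both arms it was 0.03-0.07 SD even under those unequal correlations.

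The planned sensitivity analyses help in part. Imputation that used Day 1-3 values would supply a MAR reference, but the imputation model is not described and the joint models are only possibilities. Finally, the likelihood estimator was unbiased by construction, because simulated withdrawal depended on the Day 1-3 value and nothing else related to outcome. If adverse events drive withdrawal and relate to outcome, a mixed model without them is not assured MAR validity either.

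The study describes itself as producing pilot data, and the precision gain is an efficiency argument rather than an error. Neither removes the mismatch between the assumption claimed and the tests named.

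**Conclusion.** The inconsistency is real. The SAP claims MAR for its primary and secondary analyses and uses a MAR analysis as its reference, but the tests it names are valid only under narrower conditions. Because section 7.2.1 withdraws participants for possibly drug-linked side effects, withdrawal is likely to differ by arm. It is not certain to, and the documents do not show that it will depend on outcome.

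The conclusion that the primary CBF/CVR result will be biased by a known amount does not follow. Outcomes does not say which change is primary. For change from pre-fight to Day 30, the bias is zero under the SAP's common correlation with Day 1-3-dependent dropout. For change from Day 1-3 to Day 30, the contrast the SAP names for biomarkers, it is 0.03-0.16 SD at an assumed 16% v 4% withdrawal, across correlations of 0.2 and 0.5 and weak to complete dependence on the Day 1-3 value. The change is worth making because it is cheap, defines the missing reference analysis and improves precision.

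**What to change.** 1. For CBF/CVR, and other outcomes with a pre-fight value, make the main analysis a likelihood-based repeated-measures model of Day 1-3 and Day 30. Include pre-fight baseline as covariate, with arm, visit, arm-by-visit and regimen (single dose or 14 days). Use every randomised participant with any post-injury value, and name the primary contrast.
2. Keep the two-sample t-test as a sensitivity analysis.
3. Add multiple imputation that includes Day 1-3 values and recorded adverse events or reason for withdrawal. Compare the planned pattern-mixture and shared-parameter models with this MAR reference.
4. Reconcile section 7.2.1 (withdrawal from the study), section 8.3 (headache may be treated) and the intent-to-treat statement in section 10.1, so that it is clear whether follow-up data are collected after withdrawal. No clinical rule is proposed here.
5. Reconcile the schedule table in section 7.1.1, which marks no symptom inventory at baseline, with section 7.3.2, which lists a baseline symptom questionnaire. This settles whether symptoms can be baseline-adjusted.

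Items 1 to 3 cost SAP wording and a little more analysis, and use visits already scheduled. Items 4 and 5 need protocol clarification. If the main analysis is left as it is, the MAR sentence should be replaced by the assumption the tests need: missing completely at random within arm.
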